Secondary outcomes	Occurrence of UTI in the follow-up period, change in rUTI Impact Questionnaire, antibiotic use, microbiologically-proven UTIs, antimicrobial resistance (AMR) development, prevalence of asymptomatic bacteriuria, adherence with allocated treatment, UTI severity, costs to the NHS, personal social services (PSS) and women, quality-adjusted life years (QALYs), incremental cost per QALY gained at 6 months, incremental net benefit at 12- months, incremental cost per QALY gained over a lifetime horizon, women's marginal willingness-to-pay (WTP) for the interventions and to avoid a UTI, participant satisfaction with treatment and adverse events. Interviews with healthcare practitioners (HCPs) and participants to explore trial processes, intervention mechanisms and context and to inform future implementation. Outcomes will be collected for each participant over the 6-month treatment period following randomisation and also during a follow-up period of 6-months after completion of allocated preventative treatment (making up a total study period of 12-months for each participant) and analysed at trial completion.			
Tertiary/Exploratory	Investigate the main effect of the second-stage treatment for participants			
outcomes	who did not respond to their initial treatments and identify the best sequence			
	of prophylaxis regimens that lead to the lowest UTI rate.			
Investigational	Gentamicin			
medicinal products				
Form	80mg of Gentamicin diluted to 50ml using normal saline instilled into the bladder weekly for month 1, fortnightly for Months 2 & 3 and monthly for Months 4,5 & 6* * 11 instillations			

Dose	80mg			
Route	Intravesical (directly into bladder)			
Medical device	Glycosaminoglycan (GAG) replacement compounds (Ialuril, Cystistat, Gepan,			
	etc)			
F	CAC replacement compounds //sluvil_Curtistat_Conce.sta) _1.vial of CAC			
Form	GAG replacement compounds (laluril, Cystistat, Gepan, etc) – 1 vial of GAG			
	replacement. compound instilled into the bladder weekly for month 1,			
	fortnightly for Months 2 & 3 and monthly for Months 4,5 & 6*			
	* 11 instillations			
Dasa	A C month regime of institutions will be used. The variance is been done the			
Dose	A 6-month regime of instillations will be used. The regime is based on the			
	protocol used at the lead site. The volumes of the chosen GAG replacement			
	options are Cystistat [®] 50ml, Ialuril [®] 50ml and Gepan [®] 40ml.			
Route	Intravesical (directly into bladder)			

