analysis identified no randomised trials (RCTs) of intravesical antibiotics and two small RCTs for intravesical GAG replacement compounds (n=26, n=54)⁹. Despite this paucity of high-level evidence our recent survey conducted via the UK Continence Society found that 76% of specialists regularly use intravesical treatments in their everyday practice. There appears to be a significant disparity between the widespread clinical use of these treatments and the evidence required to justify this. A recent overview in this topic area highlighted the use of intravesical preventative treatments as a potential future therapy and stated that "high local concentrations of antibiotic at the urothelial surface can be achieved by direct instillation into the urinary tract". The authors noted that "only the performance of clinical trials in the appropriate patient populations can properly appraise the potential of intravesical therapy for UTI"¹⁰. There is clearly an urgent need for a well-designed trial to demonstrate the relative effectiveness of the 2 most commonly used intravesical treatments and compare this to the current guideline-recommended treatment of second line daily oral antibiotics. VESPER, a 3-arm RCT designed to assess the relative effectiveness and cost-effectiveness of two intravesical preventative treatments, Gentamicin and GAG replacement compounds, against guidelinerecommended second-line daily oral tablet antibiotic prophylaxis will directly address this evidence gap. Secondary outcomes will include development of antimicrobial resistance (AMR) during treatment, total antibiotic use, patient-reported treatment satisfaction, patient-reported UTI impact¹¹, adverse events and, using economic analysis, the value of the interventions to women suffering rUTI and to the NHS.

4.1 **Rationale for current trial/Justification of Treatment Options**

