VESPER is directly aimed at infection prevention. The incidence of AMR within post-menopausal rUTI sufferers increases from 25% to >80% following prolonged antibiotics¹⁶. A systematic review and meta-analysis¹⁷ (searches up to 2009) identified a number of studies that together provide strong evidence of an association at the individual patient level between the prescribing of antibiotics in primary care and antimicrobial resistance in bacteria at different sites, including urinary tract infections, with effects lasting up to 12 months. The UK AMR strategy highlights that "we are heading rapidly towards a world in which antibiotics no longer work" due to "increased and inappropriate use" and advises that "preventing infections is essential"¹³. A recent publication details an estimated 4.95M deaths associated with AMR globally in 2019¹⁸. Urinary Tract Infections (UTIs) caused by antibioticresistant bacteria are difficult to treat and often recur. They also account for a staggering 50% of all known cases of sepsis¹³. For example, unplanned hospital admissions secondary to UTIs cost £434 million in 2013/2014. The frequent UTI sepsis complication is well-recognised and is noted within the NHS Long Term Plan as a key problem to be tackled. The goal is to reduce Gram-negative sepsis by 2024/25 and focus on UTIs as they are a leading cause of bloodstream infections¹⁹. The key causative organisms of both UTIs and urosepsis are *E. coli* (~50%) and Klebsiella (~15%)²⁰. Worryingly, extendedspectrum Beta-Lactamase (ESBL) producing *E. coli* and Klebsiella species are increasingly common, and are included in the World Health Organisation 'priority pathogens' list²¹.

VESPER is designed to demonstrate treatment superiority in terms of UTI reduction. The two experimental interventions in our study both have potential to reduce AMR by limiting UTI occurrence and consequent systemic antibiotic exposure which would be a major benefit to public health. Although one experimental arm is an antibiotic, it is unlikely to affect the gut flora as it is administered directly into the bladder and not absorbed systemically due to the low permeability of the urothelium which lines the urinary tract. Previously published work from co-applicants has shown that gentamicin is undetectable in the bloodstream of patients who receive it intravesically.^{22, 23}.

Canolfan

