- Population-level summary: Incidence rate ratio from Poisson or negative binomial regression model for intravesical treatments and second-line oral antibiotic prophylaxis arms.

Rationale for estimand: To compare the strategy of initially prescribing intravesical treatments compared to prescribing second-line oral antibiotic prophylaxis as would be observed in routine practice.

Sensitivity analyses around the primary outcome will consider appropriate estimands, accounting for initial allocation and reinstatement/switching of different prophylaxes via the SMART design. Weighted and replicated regression approach will be considered to evaluating adaptive intervention effects³⁴.

Secondary outcomes will also be analysed based on intention-to-treat using appropriate regression models (e.g. linear regression for continuous outcomes, Poisson/negative binomial for counted outcomes, logistic regression for binary outcomes, as appropriate), adjusting for covariate factors

used in randomisation as per the primary analysis, and are described in the Table below. Mixed-effects models will be considered when participants have multiple data points over time.

As part of our process evaluation, we will describe differences between those who opt for different modes of intravesical administration (i.e. self vs clinician-delivered), including the extent to which it varies across sites. We will also describe the timing of this decision in relation to randomisation and whether this is associated with differential response, switching, and outcomes. We will similarly describe the variability (and association with response/outcomes) in prophylaxis implementation more generally (i.e. which oral antibiotics are used in the oral antibiotic arm, switches and circumstances around switching etc.)

Table 7 - planned outcome analysis

Outcome	Measure	Time frame	Analysis
Occurrence of symptomatic UTI in the 6-month follow-up period	UTI-rate occurred after 6 months of treatment period	At 12 months	Poisson/ negative regression
Change in rUTI Impact Questionnaire	Recurrent UTI impact questionnaire	At 6 months/12 months	Linear regression
Days prescribed antibiotics	Addition antibiotic prescribed	At 6 months/12 months	Poisson/ negative regression
Microbiologically proven UTIs	Per the primary outcome plus a concomitant positive urine culture	At 6 months/12 months	Logistic regression

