AMR in E. coli isolated from urine or perineal swabs	Resistance to 1 or more antibiotics in the panel tested	At 6 months/12 months	Logistic regression
Multi-drug resistance in E. coli	Resistance to >=1 antimicrobial agent in >=3 antibiotic categories	At 6 months/12 months	Logistic regression
Asymptomatic bacteriuria	Positive urine culture without symptoms	At 6 months/12 months	Logistic regression

Canolfan

Adverse events	Type, frequency, and severity of adverse events	At 6 months/12 months	Descriptive statistics
Hospitalisation due to UTI	Number of hospitalisation due to UTI	At 6 months/12 months	Poisson / negative binomial regression
Quality of life	EQ-5D-5L	At baseline/3/6/12 months	Linear regression
Participant satisfaction	Treatment Satisfaction Questionnaire for Medication	At 6 months/12 months	Linear regression

A comprehensive Statistical Analysis Plan will be finalised by the trial statistician, with support from the Management Group (TMG), agreed by the Trial Steering Committee (TSC), and Data Monitoring and Ethics Committee (DMEC) prior to database lock and commencement of analysis. The findings will be reported in line with the Consolidated Standards of Reporting Trials (CONSORT) statement. We will incorporate the estimand framework within our protocol and statistical analysis plan, with the aim of specifying primary and sensitivity estimands and aligning analysis strategies accordingly. Our primary clinical analysis will be based on a "treatment policy" strategy of offering each of these options as second-line prophylaxis and analyse participants in the arm to which they were originally randomised within a multiple imputation framework, regardless of intravesical instillation/prophylactic oral antibiotics receipt (including treatment switching) or outcome availability.

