For trial purposes urines will be considered as indicative of UTI if they fulfil SMI B41 definitions⁵⁶ for "Probable UTI" or "Possible UTI" (see below) based on combinations of host, sample type, symptoms, WBC and CFUs. Presence of WBC where relevant to the definition will be considered as significant at a threshold of >100 WBCs/ μ L. The definitions are as follows:

Probable UTI is defined as $\geq 10^5$ CFU/ml of pure culture, irrespective of WBC levels.

Possible UTI is defined using the following criteria: re culture at ≥105 with predominant growth (where the second or third organisms are at least 3xlog₂ CFU/ml below the predominant organism) irrespective of WBC (dual culture: where both are $\geq 10^5$ or one is $\geq 10^5$ and the other is $\geq 10^4$) accompanied by WBC, pure or predominant culture at 104 - 105 accompanied WBC, predominant culture at 10⁴ - 10⁵ of a UTI pathogen species accompanied

Canolfan

by WBC OR pure or dual culture (where both present are known urinary pathogens at 10^3 – 10⁴ accompanied by WBC.

Urines with culture results of pure/predominant growth of Coagulase Negative Staphylococci at $\geq 10^4$ CFU/mL but counts of WBC<100 and SEC>100 may be excluded as likely contaminated.

Antimicrobial susceptibility testing will be performed on all significant isolates using the EUCAST Disk Diffusion method and breakpoints. For Gram-negative uropathogens the following antimicrobials will be tested: ampicillin/amoxicillin, co-amoxiclav, piperacillin/tazobactam, nitrofurantoin, trimethoprim, mecillinam, fosfomycin, cephalexin, cefixime, cefuroxime, cefpodoxime, cefotaxime, ceftazidime, ciprofloxacin, ertapenem, meropenem, temocillin, gentamicin, amikacin & co-trimoxazole. For Grampositive uropathogens, Staphylococcus aureus/saprophyticus will be tested against cefoxitin, cotrimoxazole, erythromycin, clindamycin, tetracycline, mupirocin, penicillin, gentamicin, fusidic acid, linezolid, ciprofloxacin, rifampicin, vancomycin and teicoplanin. For Enterococci, ampicillin, ciprofloxacin, nitrofurantoin, vancomycin and teicoplanin will be tested whilst penicillin, clindamycin, nitrofurantoin, vancomycin and teicoplanin susceptibility will be determined for Streptococci.

All Probable and Possible UTI pathogen isolates will be stored for future analysis at -80°C on protect beads.

Perineal swabs:

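### The Table 7 AMR measure, resistance to any one agent of the panel, dilutes arm differences in resistance to the trial's own drugs and has no stated baseline term

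*Protocol*

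**What the plan says.** The outcome is described in terms of change. The synopsis lists "antimicrobial resistance (AMR) development" among the secondary outcomes, and section 4 says "Secondary outcomes will include development of antimicrobial resistance (AMR) during treatment". Section 5.4 plans longitudinal monitoring of resistance in urinary E. coli, with samples at each UTI and at baseline, 1, 3, 6 and 12 months. It also plans to assess changing resistance in E. coli from perineal swabs at baseline, 6 and 12 months. Among its items is ecological change in species and resistance patterns.

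The analysis in section 16.1 is narrower. The Table 7 row for AMR in E. coli is a yes/no at 6 and 12 months, defined as "Resistance to 1 or more antibiotics in the panel tested" and analysed by logistic regression. A second row covers multi-drug resistance. The ecological-change item has no row.

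On covariates, section 16.1 says secondary models adjust for factors "used in randomisation as per the primary analysis, and are described in the Table below"; those factors are prior UTI frequency and menopausal status. It adds: "Mixed-effects models will be considered when participants have multiple data points over time". No baseline resistance term is named.

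On the panel, section 16.4 says "For Gram-negative uropathogens the following antimicrobials will be tested" and then lists: "ampicillin/amoxicillin, co-amoxiclav, piperacillin/tazobactam, nitrofurantoin, trimethoprim, mecillinam, fosfomycin, cephalexin, cefixime, cefuroxime, cefpodoxime, cefotaxime, ceftazidime, ciprofloxacin, ertapenem, meropenem, temocillin, gentamicin, amikacin & co-trimoxazole".

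**The concern.** An any-one-agent score has a ceiling. A woman whose E. coli is amoxicillin-resistant at entry, stays so, and becomes gentamicin-resistant during instillations scores yes throughout. The row then says nothing about the resistance her allocated drug selected for.

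This matters because the protocol argues for intravesical treatment partly on resistance. The lay summary expects much less impact on resistance than from oral antibiotics, and section 4.1 argues that intravesical gentamicin is unlikely to affect the gut flora. The scheduled urine and swab isolates could test this drug by drug, but the any-one row largely cannot in women who already carry resistance to another agent. A finding of no AMR difference between gentamicin and GAG, or between gentamicin and oral prophylaxis, could be read as evidence that instilled gentamicin does not select for resistance, when the measure had little chance of showing it.

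**Working it through.** The protocol gives no power or event-rate figure for AMR, so there is nothing of its own to reproduce.

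**Inputs from the protocol**
- Panel: counting the section 16.4 list gives 20 agents for Gram-negatives, with gentamicin the 18th. Persisting resistance to any of the other 19 is enough to score yes.
- Arm size: 175 per intravesical arm and 15% drop-out (section 15.3). 175 × 0.85 = 148.75, so about 149.

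**Assumed inputs**
- New gentamicin resistance g: 12% in the gentamicin arm, 2% in the GAG arm.
- Persisting resistance to some other agent, b: 25%, 50% or 80%, equal in both arms and independent of g.
- Every retained woman has an E. coli isolate.

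The only resistance level the protocol gives is in section 4.1: "The incidence of AMR within post-menopausal rUTI sufferers increases from 25% to >80% following prolonged antibiotics". That concerns post-menopausal women after prolonged antibiotics. It suggests a range for b but is not this trial's baseline.

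**Formulas**
- P(any-one = yes) = b + (1 − b) × g.
- Arm difference on any-one = (1 − b) × (g₁ − g₂), so the share of new gentamicin resistance hidden is b, whatever g is.
- Power, two-sided 5%, Wald: Φ(d/SE − 1.96), with SE = √[(p₁(1 − p₁) + p₂(1 − p₂))/149].

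**Results**

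| Scoring | p₁ | p₂ | Difference d | SE | d/SE | Power |
|---|---|---|---|---|---|---|
| Gentamicin-specific | 0.120 | 0.020 | 0.100 | 0.0290 | 3.45 | 93% |
| Any-one, b = 25% | 0.340 | 0.265 | 0.075 | 0.0530 | 1.41 | 29% |
| Any-one, b = 50% | 0.560 | 0.510 | 0.050 | 0.0577 | 0.87 | 14% |
| Any-one, b = 80% | 0.824 | 0.804 | 0.020 | 0.0451 | 0.44 | 6–7% |

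The last entry is 6.5% counting rejections in the right direction only, and 7.3% counting both tails.

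**Other assumed rates** (148 per arm, GAG arm at 5%)

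| Gentamicin arm | Gentamicin-specific | Any-one, b = 25% | b = 50% | b = 80% |
|---|---|---|---|---|
| 10% | 37% | 10% | 6% | 4% |
| 20% | 98% | 53% | 25% | 10% |
| 30% | about 100% | 92% | 59% | 21% |

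**Fewer isolates.** If only half the women had an E. coli isolate (75 per arm, also an assumption), the 12% v 2% case gives about 69% for gentamicin-specific scoring and 17%, 9% and 5–6% for any-one. Both measures lose power, and the ordering stays the same.

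**The case against.** **The statistical analysis plan may supply the baseline term.** Section 16.1 defers detail to it, says mixed models will be considered, and nowhere says the randomisation factors are the only covariates. Omitting a baseline covariate from a randomised comparison costs precision and does not bias it. All this stands, and the covariate is the lesser part of the point. The measure itself is already fixed in Table 7, and no covariate or repeated-measures model lets a woman who already scores yes move upward.

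**The AMR plan is wider than one row.** Section 5.4 lists change in resistance patterns, and section 16.4 tests each agent, gentamicin included. That is fair. But the pattern-change outcome has no row in Table 7, so its analysis is not stated.

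**The row scores what its own label says.** It is headed AMR in E. coli; development is the language of the synopsis, section 4 and part of section 5.4. This stands. The mismatch is between the stated aim and the scored measure.

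**A drug-neutral measure is defensible.** The oral arm uses several agents, GAG is not an antibiotic, and section 4.1 also argues from lower systemic exposure. This is a good reason to keep the any-one summary, but not to have it alone.

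**Stronger readings that a reader might infer.** One is that a woman already resistant to one drug can never register new gentamicin resistance. That requires the earlier resistance to persist in the later isolate. If the strain is replaced, she can score on gentamicin alone, though as any resistance and not as new resistance. The multi-drug row also picks up gentamicin when it adds the third category. Another is that the endpoint is known to be saturated at entry, because section 4.1 quotes more than 80%. The documents do not support this: that figure is for a different group, the trial also takes pre- and peri-menopausal women, and failed first-line treatment may be methenamine or vaginal oestrogen.

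**Conclusion.** The point holds as one of dilution. Table 7's any-one measure hides new resistance to a trial drug wherever resistance to another panel agent persists, while other parts of the protocol promise to study development and change. Randomisation still balances baseline resistance on average, so the comparison is not biased.

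The size depends on a quantity the protocol does not give. Under independence, the share hidden equals the prevalence of persisting other-agent resistance. If new gentamicin resistance arises more often in women already resistant to something else, more is hidden; if less often, less. The fall from about 93% to between 29% and 6–7% illustrates the mechanism under assumed rates and a full set of isolates. It is not a forecast. Urine susceptibility is tested only on significant isolates and swabs are optional, so real power will be lower for either measure.

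This is a secondary outcome, but it carries part of the trial's rationale and can be repaired cheaply before analysis.

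**What to change.** In Table 7:

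1. Add a row for agent-specific resistance in E. coli, for the agents the trial gives (gentamicin, nitrofurantoin, trimethoprim, amoxicillin, cefalexin). Name gentamicin resistance as a contrast for the gentamicin arm, and state that this row is the analysis of the section 5.4 resistance-pattern-change outcome. This is the essential change.
2. In the AMR and multi-drug-resistance models, add the baseline result from the same specimen type as a covariate: resistant E. coli, susceptible E. coli, or no E. coli isolated or no sample. This adds precision and does not remove the ceiling in the any-one measure.
3. Keep resistance to at least one agent of the panel as a summary.

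The cost is wording in Table 7 and the analysis plan. Baseline sampling and testing against these agents are already planned, so no new visit or assay is needed. The downsides are a few more secondary estimates, and missing baseline status where the optional swab was not given.

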16.1.1 Sub-group & interim analysis

To explore the extent to which there may be a differential intervention effects by the primary outcome, rate of symptomatic UTIs from randomisation to 6-months, the model fitted for the primary analysis will be extended by including a main and treatment group interaction term for menopausal status, previous UTI frequency, and type of failed first-line treatment. For the exploration of differential intervention effects by site, the primary analysis will be extended by allowing for different slopes across sites and compare this to the original model (random intercepts only) using the Likelihood-ratio test. Estimates from the statistical models (main effects and interaction terms) will be presented alongside 95% confidence intervals and p-values.

No formal interim analysis will be conducted.

16.2 Qualitative analysis

Interviews will be recorded (with the consent of participants), transcribed and de-identified. A proportion of the patient and HCP/TR interviews will take place during the pilot phase (around months 8-15). These interviews will be analysed using rapid qualitative analysis to feedback on issues around recruitment and acceptability. The entire dataset of interviews will then be analysed using a thematic approach^{35, 36} to identify inductive and deductive themes (including themes relating directly to our interview questions as well as themes which interviewees initiate and had not been pre-empted). The thematic framework will be discussed and refined by experienced qualitative researchers. A proportion of the data will be double-coded, and discrepancies discussed to enhance analysis and vigour. NVivo coding software will be used to manage the data. The qualitative and quantitative data relating to the process evaluation (e.g. acceptability, adherence, implementation) will be brought together during interpretation (data triangulation) with members of the qualitative, quantitative and wider trial team discussing, reflecting upon, and integrating findings (investigator triangulation) to produce an overall mixed methods process evaluation.

As part of our process evaluation, we will describe differences between those who opt for different modes of intravesical administration (i.e. self vs clinician-delivered), including the extent to which it varies across sites. We will also describe the timing of this decision in relation to randomisation and whether this is associated with differential response, switching, and outcomes. We will similarly describe the variability (and association with response/outcomes) in prophylaxis implementation more generally (i.e. which oral antibiotics are used in the oral antibiotic arm, switches and circumstances around switching etc.)

